7.3.1.2 Scanning: MRI Scanning Procedure

MRI measures of white matter lesional activity (i.e., new/enlarging T2 lesions, T1 hypointense or Gd-enhancing T1 lesions) and those of brain atrophy (i.e., percentage of brain volume change) have shown to be valid surrogate endpoints for clinical outcomes. Advanced MRI techniques, such as MTR may provide higher pathological specificity for the more destructive aspects of the disease (i.e., demyelination and neuroaxonal loss) and be more closely associated with clinical correlates (Wattjes MP et al, 2015).

The principal primary outcome measure will be the number of CUA lesions. CUA lesions, which combines the high sensitivity of T1 activity with the greater specificity for permanent lesions of T2 activity, has been chosen as the best single indicator of MS activity. The following MRI parameters will be measured for all subjects for each scan obtained during the trial:

- Active lesions defined as T1 gadolinium-enhancing lesions, or new T2 non-enhancing or enlarging T2 lesions during each pre-defined period (designated “CUA MRI lesions”)
- T1 hypointense lesions
- Brain volume
- MTR

The MRI scan will also be evaluated for safety assessment to rule out PML or any serious central nervous system disease (e.g., tumor, stroke etc).

All scans will be performed according to a standard protocol detailed in a separate MRI scan user’s manual. A central imaging core lab will perform the analysis of all MRI scans. As with other laboratory tests and clinical measures, strict adherence to the MRI scanning protocol, and prompt handling of the scans is essential in obtaining a meaningful result.

Prior to subject assessment, each trial site will be asked to send a ‘test’ or ‘dry-run’ scan to assess image quality and shipment procedures, to evaluate the accessibility of the electronic data carrier, and to assess the ability to correctly reposition subjects so as to get comparable brain images. Only upon final approval of this test scan, will sites be allowed to begin assessing subjects.

Each subject should be scanned using the same machine throughout the trial.

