8.5 Description of Statistical Analyses

8.5.1 General Considerations

All analyses of all endpoints except the primary analysis, will be performed exploratively and, differences with a p-value of 0.05 or less will be considered nominally statistically significant.

Parameter estimates with associated 95% confidence intervals (CIs) will be reported in each analysis. No correction for multiple testing will be applied for any secondary or tertiary analysis.

Subjects' demographic factors and baseline clinical characteristics will be summarized with the following measures: mean with standard deviation, minimum and maximum for normally distributed continuous variables, median with interquartile range, minimum and maximum for other continuous variables and counts with percentages for categorical variables.

As the secondary and tertiary analysis set concerns repeated measurements of outcomes for each individual, it is likely that observations pertaining to each individual will be correlated. Furthermore, as this is a multi-center trial, it is likely that clustering of individuals within trial sites will produce an additional source of correlation. Mixed-effects regression, whereby a three-level hierarchical model is specified for observations within subjects within trial sites, will be used to account for within-subject and within-center correlation (Gibbons, 2010).

The parametric assumptions underlining the regression models specified will be examined. Should these assumptions be violated, alternative methods, such as non-parametric approaches, may be considered in addition.

Assessment Schedules

It is likely that the second year treatment may be delayed substantially due to grade 3 or 4 lymphopenia for a small number of subjects for whom the second dose is not required immediately. Due to the need for a finite follow-up period, a buffer of 3 months is given for subjects who do not receive the second treatment at the specified time. Subjects for whom treatment is delayed by over 3 months may not have all assessment data captured and as such, these observations will be treated as missing in efficacy analyses.

In each analysis, should assessment be delayed, subjects' assessment data will be treated as though it occurred at the time point specified and inferences will be conducted accordingly.

Missing Data

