8.5.3 Analysis of Secondary and Tertiary Endpoints

Analysis comparing continuous secondary and tertiary endpoints measured repeatedly at specific time points to baseline will be undertaken using similar techniques to those outlined for the primary analysis while taking the within-subject correlation into account where appropriate. Linear regression modelling assumes that outcomes are normally distributed. Appropriate transformations (such as square root or log transform) may be used to achieve normality. Alternatively, nonparametric methods may be applied.

Annualized relapse rate will be evaluated using a Poisson regression model with count of relapses as dependent variable and with age and EDSS as covariates. The log of time under

observation (in days) will be the offset variable in the model. Categorical endpoints will be analyzed by logistic regression.

Safety endpoints will be summarized descriptively, providing detail of the frequency, type, severity and outcome of the events.

Other outcomes will be summarized descriptively.

CCI

CCI

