The estimated annualized CUA lesion count will be calculated based on the observed margin of the corresponding analysis set at Baseline.

Generalized linear model assuming negative binomial distribution

The annualized CUA lesion count will be evaluated using a generalized mixed-effects linear model with log link function assuming a negative binomial distribution. Period (i.e. Baseline Period, each post-Baseline Period as specified above) will be analyzed as: a) a repeated factor accounting for time between scans (in years) if the time is different between scans, or b) neglected, if the time between scans is constant (for example: for every 6 months Periods, 1 yearly Periods); and within subject correlation using an unstructured covariance matrix. Age and EDSS at Baseline (≤ 3 , > 3) will be used as fixed effect covariates.

The ratio of the annualized CUA lesion count of each post-Baseline Period versus the Baseline Period will be calculated as the inverse log of the difference of the estimated contrast between each post-Baseline Period and the Baseline Period.

Offset will be applied if needed.

The estimates, standard deviation and 95% confidence intervals for the annualized CUA lesion count at each Period and the ratio between Periods will be presented together with the estimated fixed effects. If the model doesn't converge an alternative covariance structure will be used instead of the unstructured covariance matrix.

The estimated annualized CUA lesion count will be calculated based on the observed margin of the corresponding analysis set at Baseline.

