14.3.10 Magnetization Transfer Ratio (MTR)

Analysis (Analysis Set)	Derivation	Statistical Analysis Methods	Missing data handling
Tertiary endpoint: Change from Baseline in MTR percentage			
Tertiary (FAS)	Change from Baseline in MTR - White Matter (%) at Month 24 Visit.	Mixed-effects linear model for the change from Baseline with the following adjusting factors: 
 • Baseline score, • Age (in years), • EDSS at Baseline (≤ 3, > 3), • Time between scans (years), • Within-subject correlation. Estimated Least Square Means (LS Means) and corresponding Standard Errors (SE) will be presented by Visit including 2-sided p-values and 95% CI	Missing observations at Baseline: Subjects with a missing Baseline MTR will not be included in the linear model. Missing post-Baseline observations: Missing post-Baseline assessments will not be imputed. The repeated measurement model handles missing post-Baseline assessments under the assumption of MAR.
	Change from Baseline in MTR - Grey Matter (%) at Month 24 Visit.		
	Change from Baseline in MTR - T1 lesions (%) at Month 24 Visit.		
	Change from Baseline in MTR - T2 lesions (%) at Month 24 Visit.		
	Change from Baseline in MTR - T2 perilesions (%) at Month 24 Visit.		
	Change from Baseline in MTR - Putamen (%) at Month 24 Visit.		
	Change from Baseline in MTR - Thalamus (%) at Month 24 Visit.		
	Change from Baseline in MTR - Optic Nerve (%) at Month 24 Visit.		
Tertiary endpoint: Change from Month 6 Visit in MTR percentage			
Tertiary (FAS)	Change from Month 6 Visit in MTR - White Matter (%) at Month 24 Visit.	Descriptive summary statistics.	
	Change from Month 6 Visit in MTR - Grey Matter (%) at Month 24 Visit.		
	Change from Month 6 Visit in MTR - T1 lesions (%) at Month 24 Visit.		
	Change from Month 6 Visit in MTR - T2 lesions (%) at Month 24 Visit.		
	Change from Month 6 Visit in MTR - T2 perilesions (%) at Month 24 Visit.		
	Change from Month 6 Visit in MTR - Putamen (%) at Month 24 Visit.		
	Change from Month 6 Visit in MTR - Thalamus (%) at Month 24 Visit.		
	Change from Month 6 Visit in MTR - Optic Nerve (%) at Month 24 Visit.		

Mixed-effects linear model for repeated measures

As defined in Section 14.3.1 applying adaptations to the endpoints, factors and covariates listed in the table above.

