Tertiary (FAS)	Annualized PBVC at Month i Visit, where i=1, 2, 3, 6, 12 and 24.	Mixed-effects linear model for repeated measures for the change from Baseline with the following adjusting factors: 
 • Baseline value, • Age (in years), • EDSS at Baseline (≤ 3, > 3), • Visit, • Time between scans (years), • Within-subject correlation. Estimated Least Square Means (LS Means) and corresponding Standard Errors (SE) will be presented by Visit including 2-sided p-values and 95% CI.	Missing observations at Baseline: Subjects with a missing Baseline brain volume will not be included in the linear model. Missing post-Baseline observations: Missing post-Baseline assessments will not be imputed. The repeated measurement model handles missing post-Baseline assessments under the assumption of MAR.
	Annualized PBVC 
 • $\leq -0.4\%$ • $> -0.4\%$ during the Treatment Period.	Descriptive summary statistics.	
Tertiary endpoints: Annualized percentage white matter brain volume change from Baseline			
Tertiary (FAS)	Annualized PWMBVC at Month 24 Visit.	Descriptive summary statistics.	
	Annualized PWBVC 
 • $\leq -0.4\%$ • $> -0.4\%$ at Month 24 Visit.		

Tertiary endpoints: Annualized percentage grey matter brain volume change from Baseline			
Tertiary (FAS)	Annualized PGMBVC at Month 24 Visit.	Descriptive summary statistics.	
	Annualized PGMBVC 
 • ≤ -0.4% • > -0.4% at Month 24 Visit.		
Tertiary endpoints: Annualized percentage deep grey matter brain volume change from Baseline			
Tertiary (FAS)	Annualized PDGMBVC change at Month 24 Visit.	Descriptive summary statistics.	
	Annualized PDGMBVC 
 • ≤ -0.4% • > -0.4% at Month 24 Visit.		
Tertiary endpoints: Percentage brain volume change from Baseline			
Tertiary (FAS)	PBVC change at Month 24 Visit.	Descriptive summary statistics.	
Tertiary endpoints: Percentage white matter brain volume change from Baseline			
Tertiary (FAS)	PWMBVC change at Month 24 Visit.	Descriptive summary statistics.	
Tertiary endpoints: Percentage grey matter brain volume change from Baseline			
Tertiary (FAS)	PGMBVC change at Month 24 Visit.	Descriptive summary statistics.	
Tertiary endpoints: Percentage deep grey matter brain volume change from Baseline			
Tertiary (FAS)	PDGMBVC change at Month 24 Visit.	Descriptive summary statistics.	

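### The annualized brain-volume, Month 24 MTR and tertiary lesion-ratio models leave out the center level that the protocol commits to, without disclosure; if change scores correlate within center, the brain-volume and MTR intervals are too narrow

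*SAP*

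**What the plan says.** Protocol 8.5.1 expects correlation within trial sites as well as within subjects. For repeated secondary and tertiary outcomes it states that "a three-level hierarchical model is specified for observations within subjects within trial sites, will be used to account for within-subject and within-center correlation". Protocol 8.5.3 adds that continuous secondary and tertiary endpoints will be analyzed "using similar techniques to those outlined for the primary analysis while taking the within-subject correlation into account where appropriate". The primary technique in Protocol 8.5.2 accounts for correlation within center or region.

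The SAP leaves center out of three tertiary model families:

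- **Annualized PBVC (14.3.11).** After "Mixed-effects linear model for repeated measures for the change from Baseline with the following adjusting factors" the list gives baseline value, age, EDSS and visit, and ends with "Time between scans (years), • Within-subject correlation".
- **MTR (14.3.10).** After "Mixed-effects linear model for the change from Baseline with the following adjusting factors" the list gives baseline score, age, EDSS, time between scans and within-subject correlation. It is modeled at Month 24 only.
- **Tertiary negative binomial ratios (14.3.1, carried to T1 Gd+ in 14.3.3 and active T2 in 14.3.7).** The text models within-subject covariance and says "Age and EDSS at Baseline (≤ 3 , > 3) will be used as fixed effect covariates".

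Other SAP models keep center. Pooled center is an adjusting factor in the tertiary linear models for CUA change. By cross-reference it also enters those for T1 Gd+, active T2, 9HPT and T25FW. The 6-month negative binomial sensitivity model in 14.1.2 keeps within-pooled-center correlation. SAP Section 7, which lists departures from the protocol and includes one on MTR, says nothing about center.

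**The concern.** The protocol names a correlation structure, and the SAP drops one level of it for some endpoints, keeps it for others, and gives no reason.

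The design makes this matter for mean changes. PBVC and MTR are reported as single-arm LS-mean changes with two-sided p-values and 95% confidence intervals. With no control arm, a center effect on the change does not cancel between groups. It adds to the variance of the mean, and a model without center leaves it out of the standard error. At stake are the stated precision and the nominal significance of the brain-volume and MTR results.

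**Working it through.** The readable text gives no ICC and no standard error for these endpoints. The sample-size section and the statistics-assumptions appendix are blacked out, which is not a fault of the plan. There is thus no figure to reproduce, and the size is shown as a range over assumptions.

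**Inputs from the documents.** N = 265 and about 80 sites (Protocol synopsis), so m = 265/80 = 3.31 subjects per site. The synopsis names 16 countries, so 265/16 = 16.56 per country. The nominal level is 5% two-sided (Protocol 8.5.1).

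**Assumed.** The ICC of the change score, and the coefficient of variation (cv) of site size.

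**Formulas.** Design effect DE = 1 + (m(1 + cv²) − 1) × ICC. The true standard error exceeds the reported one by √DE. The actual rejection rate under no change is 2 × P(Z > 1.96/√DE).

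Example, equal sites, ICC 0.05: DE = 1 + 2.31 × 0.05 = 1.116 and √DE = 1.056. With cv 0.7: DE = 1 + (3.31 × 1.49 − 1) × 0.05 = 1.197 and √DE = 1.094.

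| ICC of change | Factor, equal sites | Rejection | Factor, cv 0.7 | Rejection |
|---|---|---|---|---|
| 0 | 1.000 | 5.0% | 1.000 | 5.0% |
| 0.01 | 1.011 | 5.3% | 1.019 | 5.5% |
| 0.05 | 1.056 | 6.4% | 1.094 | 7.3% |
| 0.10 | 1.110 | 7.7% | 1.180 | 9.7% |

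If the correlation sat at country level (16 equal clusters), ICC 0.05 gives DE = 1 + 15.56 × 0.05 = 1.778, a factor of 1.33 and 14.2% rejection.

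**Simulation of a mean change** (4,000 trials per setting, 80 sites, size cv about 0.7), coverage of the 95% interval:

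| ICC of change | Center ignored | Center fixed | Site-clustered SE |
|---|---|---|---|
| 0 | 95.6% | 95.4% | 95.0% |
| 0.05 | 92.4% | 91.6% | 94.6% |
| 0.10 | 89.6% | 87.3% | 94.6% |

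A fixed center factor evaluated at the observed margin does not help, because it takes between-center variance out of the standard error of the overall mean. With only 16 clusters, the clustered interval itself covered 90.8% to 92.7%.

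**Simulation of the post/baseline ratio** (baseline mean 2, true ratio 0.5, dispersion 0.5, between-subject log SD 0.7, all assumed), using subject-level pairing only:

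- 80 sites, center-level log SD 0, 0.3 and 0.5, no center-by-period variation: coverage 93.8%, 94.6% and 94.6%. The center level cancels within subject.
- Center-by-period log SD 0.2 and 0.3 (center-level SD 0.3): coverage 93.2% and 93.8% with 80 sites, and 89.4% and 85.4% with 16 clusters.

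**The case against.** **The MTR section may import center by cross-reference.** It ends with "As defined in Section 14.3.1 applying adaptations to the endpoints, factors and covariates listed in the table above", and the 14.3.1 linear models include pooled center. But the same sentence adapts the model to the section's own table, which has no center. The PBVC section has no such cross-reference.

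**MTR is not a repeated outcome in the SAP.** This stands. With one modeled change per subject at Month 24, the three-level sentence in 8.5.1 does not directly reach MTR. Its link to the protocol is 8.5.3.

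**Within-center correlation of change is unproven.** This stands too. A reader might infer that scanner drift or upgrades make a site's subjects move together. The protocol says only "Each subject should be scanned using the same machine throughout the trial", which fixes the machine per subject and not per site, and drift is not mentioned. Dry-run scans, a standard protocol, central quality checks and central joint image comparison for PBVC all work against such effects. So narrowness is conditional.

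**The country-level figure is not the main case.** A reader might take 14% rejection as the size of the problem. That applies ICC 0.05 to mostly country-level clusters, while 8.5.1 names trial sites. SAP Section 9 keeps sites with more than 12 subjects separate and merges some small countries, so 16 is not the SAP's number of pooled centers. To give a design effect of 1.78, the ICC among equal sites would have to be about 0.778/2.31 = 0.34.

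**The endpoints are exploratory.** True: Protocol 8.5.1 makes all non-primary p-values nominal, and no decision rule depends on them.

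**Conclusion.** The omission is real. It departs from Protocol 8.5.1 for PBVC and the repeated ratio outcomes, and from 8.5.3 for MTR. It is inconsistent with other models in the same SAP and is not disclosed in Section 7.

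For PBVC and MTR the intervals are too narrow if, and only if, change scores correlate positively within center. At site level the understatement runs from about 1% to 18% of the standard error for ICC 0.01 to 0.10 and size cv 0 to 0.7. A nominal 5% test then rejects about 6% to 7% at ICC 0.05 and 8% to 10% at ICC 0.10. It would be materially larger only if the correlation sat at country or pooled-center level.

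A reader might extend the same claim to the lesion ratios. The documents do not support that. Each subject is its own control, so with the pairing modeled as 14.3.1 describes, a shared center level cancels. Only center-by-period variation would narrow those intervals. The point covers the tertiary ratio models only, since the 6-month negative binomial model keeps center.

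The primary test is untouched. This is a minor correction with a clear protocol basis.

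**What to change.** - **PBVC (14.3.11) and MTR (14.3.10):** add a random site effect, which is the level named in Protocol 8.5.1, or use site-clustered robust standard errors. A random pooled-center effect is a second choice. Clustering on few pooled centers would need a small-sample correction, given the coverage seen with 16 clusters.
- Do not copy pooled center from 14.3.1 as a fixed factor. It does not restore coverage of a single-arm mean.
- **Tertiary negative binomial ratios (14.3.1, 14.3.3, 14.3.7):** use center-clustered standard errors or a center-by-period random effect. A random center intercept alone would leave these intervals essentially unchanged.
- If center is left out of the ratio models on purpose, record and justify that in SAP Section 7.

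The cost is a term or standard-error option in five SAP sections and their programs. Intervals on exploratory endpoints become somewhat wider. With about three subjects per site the random-effect models may be slow to converge, so the clustered standard error should be named in advance as the fallback.

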14.3.12 No Evidence of Disease activity

No Evidence of Disease activity (NEDA), also referred to as freedom from disease activity, is a new goal that is emerging in MS treatment. NEDA is a composite measure of disease activity, including relapses, cognition and disability progression, and MRI activity. Since MRI activity is a broad concept, which can correspond to the MRI lesion load or changes in brain volume monitoring brain atrophy, the distinction between NEDA-3 and NEDA-4 will be provided.

NEDA-3

NEDA-3 at Month 24 is defined by the absence of:

- Qualifying Relapses,
- 6-months Confirmed Disability Progression (6MCDP),
- MRI activity,

during the whole Treatment Period. If the information for one of the components is unknown, and none of the other components are observed, NEDA-3 will be classified as “unknown”. Thus, NEDA-3 can be derived from its components as follows:

- Yes: all components = “No”,
- No: at least one of the components =” Yes”,
- Unknown: Otherwise.

NEDA-3 (frequent MRI)

NEDA-3 at Month 24 is defined by the absence of:

- Qualifying Relapses,
- 6-months Confirmed Disability Progression (6MCDP),
- MRI activity (frequent MRI),

during the whole Treatment Period. If the information for one of the components is unknown, and none of the other components are observed, NEDA-3 will be classified as “unknown”. Thus, NEDA-3 can be derived from its components as follows:

- Yes: all components = “No”,
- No: at least one of the components =” Yes”,
- Unknown: Otherwise.

NEDA-4

NEDA-4 at 24 Month is defined as the composite endpoint of NEDA-3 and the absence of brain atrophy.

NEDA-4 (frequent MRI)

NEDA-4 (frequent MRI) at Month 24 is defined by the composite endpoint of NEDA-3 (frequent MRI) and the absence of brain atrophy.

Qualifying Relapse

- Yes: qualifying relapses reported during the Treatment Period,
- No: study completed, and no qualifying relapse reported during Treatment Period,
- Unknown: otherwise.

6-Months Confirmed Disability Progression (6MCDP)

A Sustained Increase in EDSS score, is defined by an increase of:

- at least 1.5 points if the Baseline EDSS score was 0, or
- at least 1 point if Baseline EDSS score was between 0.5 and 4.5 inclusively, or
- at least 0.5 point if the Baseline EDSS score was at least 5,

that occurs over a 6-month time Period.

The increase will be defined as sustained when it occurs on two post-Baseline Visits, which are at least 166 days (6 months × 30 - 14 days Visit Window) apart and no observations at any other Visit (including unscheduled Visits) in between are less than the defined increase.

The occurrence of a 6MCDP is defined as:

- Yes: sustained increase in EDSS score that started during the Treatment Period,
- No: at least 2 post-Baseline EDSS assessments that are 166 (or more) days apart are available and no sustained EDSS progression that started during the Treatment Period,
- Unknown: Otherwise.

Start date of the 6MCDP is the start date of the first sustained increase in EDSS.

MRI activity:

- Yes: At least one T1 Gd+ at any scan assigned to Month 6, Month 12, Month 18, Month 24 Visit, or at least one active T2 during any of the following Periods: Baseline to Month 6, Month 6 - Month 12, Month 12 - Month 18, Month 18 – Month 24 Visits.
- No: T1 Gd+ = 0 at all scans assigned to Month 6, Month 12, Month 18, Month 24 Visit that have a value and at least one T1 Gd+ value from Month 18 or Month 24 Visit available, and all active T2 = 0 during any of the following Periods: Baseline - Month 6, Month 6 - Month 12, Month 12 - Month 18, Month 18 - Month 24 Visits that have a value and at least one active T2 value from periods Month 12 - Month 18 or Month 18 - Month 24 Visits available.
- Unknown: Otherwise.

CCI [REDACTED]

[REDACTED]

[REDACTED]

[REDACTED]

CCI [REDACTED]

CCI [REDACTED]

Brain Atrophy

- Yes: Annualized percentage brain volume change during the Treatment Period < -0.4% (see Section 14.3.11),
- No: Annualized percentage brain volume change during the Treatment Period ≥ -0.4%,
- Unknown: Otherwise.

Analysis of NEDA

NEDA and its components will be analyzed with a logistic regression with adjusting factors age (in years) and EDSS at Baseline (≤3, >3).

Analysis (Analysis Set)	Derivation	Statistical Analysis Methods	Missing data handling
Tertiary endpoint: NEDA at 24 months			
Tertiary (FAS)	NEDA-3 during Treatment Period	Logistic regression: Adjusting factors: 
 • Age (in years), • EDSS at Baseline (≤3, >3). Estimated probability and corresponding Standard Errors (SE) will be presented including 2-sided p-values and 95% CIs.	Unknown status: Subjects with an unknown status will be excluded from the logistic regression. Missing covariate or stratification information will be imputed as specified in Section 9.
Tertiary (FAS)	NEDA-3 (frequent MRI) during Treatment Period		
Tertiary (FAS)	NEDA-4 during Treatment Period		
Tertiary (FAS)	NEDA-4 (frequent MRI) during Treatment Period		
Tertiary (FAS)	Any 6MCDP during Treatment Period		
Tertiary (FAS)	Any MRI activity during the Treatment Period		
Tertiary (FAS)	Any MRI activity (frequent MRI) during the Treatment Period		
Tertiary (FAS)	Brain Atrophy during Treatment Period		
Tertiary (FAS)	Any Qualifying Relapse during the Treatment Period		

All components of NEDA will be listed by subject.

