7.3.2.2 Expanded Disability Status Scale (EDSS)/Kurtzke Functional System (KFS)

The neurological examination, EDSS/KFS will be obtained at the Pre-Baseline, Baseline, and at the end of 6, 12, 18 and 24 months (see [Appendix 7: Kurtzke Functional System](#), and [Appendix 8: Expanded Disability Status Score \(EDSS\)](#)).

Definition of EDSS Progression

An EDSS progression is defined as an increase in the EDSS scale as follows:

- If the Baseline EDSS score is 0, the increase must be ≥ 1.5 units
- If the Baseline EDSS score is ≥ 0.5 or ≤ 4.5 , the increase must be ≥ 1.0 units
- If the Baseline EDSS score ≥ 5.0 the increase must be ≥ 0.5 units

A confirmed EDSS progression is defined as EDSS progression (as defined above) confirmed after 3 months.

7.3.2.3 9-Hole Peg Test (9HPT)

The 9-Hole Peg Test (9HPT) is considered as a gold standard measure of manual dexterity and most frequently used in MS research and clinical practice. The 9HPT requires participants to repeatedly place and then remove nine pegs into nine holes, one at a time, as quickly as possible (Feys P et al, 2017). The 9HPT should be completed at Pre-Baseline, Baseline and then at the end of Months 6, 12 18, and 24 to measure the level of disability over time.

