14.3.13 No Evidence of Progression or Active Disease

No Evidence of Progression or Active Disease (NEPAD) is a composite measure, evolution of NEDA-3, including relapses and different measurements of disability progression and MRI activity.

NEPAD at Month 24 is defined as the composite endpoint of NEDA-3 and the absence of:

CCI [REDACTED]

CCI [REDACTED]

- 20% progression on T25-FW,
- 20% progression on 9HPT,

during the Treatment Period.

20% confirmed T25FW progression

20% confirmed progression on T25FW is defined by an increase of at least 20% from T25FW Baseline that is sustained over a 6-month time Period.

The increase will be defined as sustained when it occurs on two post-Baseline Visits, which are at least 166 days (6 months * 30 -14 days Visit Window) apart and no score at any other Visit including unscheduled Visits in between is less than the defined increase.

The occurrence of a 20% confirmed T25FW progression is defined as:

- Yes: sustained T25FW progression that started during the Treatment Period.
- No: at least 2 post-Baseline T25FW assessments that are 166 (or more) days apart are available and no sustained T25FW progression that started during the Treatment Period.
- Unknown: Otherwise.

Only T25FW assessments with the same assistance devices as at Baseline will be analyzed. T25FW trials which couldn't be finished by the subjects will be imputed with 3 minutes (see Section 14.3.17).

20% confirmed 9HPT progression

20% confirmed progression on 9HPT is defined by an increase of at least 20% from 9HPT Baseline that is sustained over a 6-month time Period.

The increase will be defined as sustained when it occurs on two post-Baseline Visits, which are at least 166 days (6 months * 30 - 14 days Visit Window) apart and no score at any other Visit including unscheduled Visits in between is less than the defined increase.

The occurrence of a 20% confirmed 9HPT progression is defined as:

- Yes: sustained 9HPT progression that started during the Treatment Period.
- No: at least 2 post-Baseline 9HPT assessments that are 166 (or more) days apart and no sustained 9HPT progression that started during the Treatment Period.
- Unknown: Otherwise.

Analysis of NEPAD

NEPAD will be analyzed with a logistic regression with adjusting factors age (in years) and EDSS at Baseline (≤ 3 , >3).

Analysis (Analysis Set)	Derivation	Statistical Analysis Methods	Missing data handling
Tertiary endpoint: NEPAD at 24 months			

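### The stand-alone EDSS, T25FW and 9HPT progression proportions count subjects followed only to Month 12 as progression-free under a 24-month heading, with no allowance for follow-up

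*SAP*

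**What the plan says.** **Schedule.** Protocol 7.3.2.2 states that "EDSS/KFS will be obtained at the Pre-Baseline, Baseline, and at the end of 6, 12, 18 and 24 months". Protocol 7.3.2.3 and 7.3.2.4 give the same visits for 9HPT and T25FW. Each measure therefore has four planned post-Baseline assessments.

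**Progression rule.** SAP 14.3.12 calls an EDSS increase sustained when it is present at two post-Baseline visits "at least 166 days (6 months × 30 - 14 days Visit Window) apart", with nothing lower in between. The No category requires that "at least 2 post-Baseline EDSS assessments that are 166 (or more) days apart are available" and that no sustained increase began in the Treatment Period. SAP 14.3.13 repeats this for T25FW ("at least 2 post-Baseline T25FW assessments that are 166 (or more) days apart are available") and 9HPT ("at least 2 post-Baseline 9HPT assessments that are 166 (or more) days apart and no sustained 9HPT progression"). All else is Unknown.

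**Analysis.** The table in SAP 14.3.12 is headed NEDA at 24 months and has its own row, "Any 6MCDP during Treatment Period". SAP 14.3.13 has matching rows for T25FW and 9HPT under NEPAD at 24 months. Each is a logistic regression on age and Baseline EDSS category. Only subjects with Unknown status are excluded.

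**Delayed Course 2.** SAP Section 9 treats efficacy data after the Course 1 Treatment Period as missing when Course 2 starts late or never starts. If it never starts, that period ends 457 days after the start of Course 1, or at discontinuation if earlier.

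**Other components.** The relapse rule reads "No: study completed, and no qualifying relapse reported during Treatment Period". MRI No requires a T1 Gd+ value from Month 18 or 24 and an active T2 value from a period ending at Month 18 or 24.

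**The concern.** A proportion under a 24-month heading will be read as a 24-month risk. For the three disability measures, however, the denominator mixes subjects seen for two years with subjects seen for one, and all of those without confirmed worsening count equally as No. The neighbouring relapse and MRI components both have a follow-up condition, and the annualized relapse rate in SAP 14.3.18 uses a follow-up offset. The disability components have neither.

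Drop-outs are not the only subjects affected. Under Protocol 5.5.1, subjects who stop cladribine continue scheduled visits. A subject who never starts Course 2, worsens at Month 18 and is confirmed at Month 24 has both values set to missing and is coded No on Months 6 and 12.

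In a single-arm trial there is no comparator carrying the same error. Measured against 24-month risk, the error runs towards fewer progressions.

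**Working it through.** **1. The plan's own figure.** The confirmation interval is 6 × 30 − 14 = 166 days, which reproduces.

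**2. Applying the rule.** At 30 days per month (SAP Section 9), planned visits fall on days 180, 360, 540 and 720. For subjects with no worsening seen:

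| Visits available | Status | Days unobserved to day 720 |
|---|---|---|
| none | Unknown | 720 |
| Month 6 | Unknown | 540 |
| Months 6, 12 | No | 360 |
| Months 6, 12, 18 | No | 180 |
| all four | No | 0 |

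Of the 16 possible availability patterns, the 11 with two or more visits (6 + 4 + 1) give No and the other 5 give Unknown. The affected leavers are normally those who go after Month 12. Someone with Month 6 and a later early-termination or unscheduled assessment at least 166 days on also qualifies.

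**3. Course 2 never started.** The efficacy cut-off is day 457 (360 + 90 + 7). Month 18 (day 540) lies beyond it, so only Months 6 and 12 remain and the status is No.

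**4. Illustrative size.** The documents give no dropout or progression rate, so the inputs are assumptions:
- p = true proportion with onset at Month 6, 12 or 18, the three visits from which confirmation is possible by Month 24
- onset even across those visits, so h = 1 − (1 − p)^(1/3) per visit
- d = fraction followed only to Month 12, for whom only a Month 6 onset can be confirmed
- leaving unrelated to progression

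Reported proportion = (1 − d)p + d·h.

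For p = 12%, h = 1 − 0.88^(1/3) = 4.17%:
- d = 10%: 0.9 × 12 + 0.1 × 4.17 = 11.2%
- d = 20%: 0.8 × 12 + 0.2 × 4.17 = 10.4%
- d = 30%: 0.7 × 12 + 0.3 × 4.17 = 9.7%

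| True p | h | d = 10% | d = 20% | d = 30% |
|---|---|---|---|---|
| 8% | 2.74% | 7.5% | 6.9% | 6.4% |
| 12% | 4.17% | 11.2% | 10.4% | 9.7% |
| 20% | 7.17% | 18.7% | 17.4% | 16.2% |

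The relative shortfall is d(1 − h/p). The factor 1 − h/p is 0.66, 0.65 and 0.64 for p = 8, 12 and 20%, so the shortfall is about two thirds of d whatever p is. At p = 12% it is about 6.5 / 13 / 20% in relative terms.

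**5. Candidate remedies in the same model.**
- *Kaplan-Meier.* Subjects followed to Month 12 contribute to the Month 6 risk set and are then censored. The estimate is 1 − (1 − h)³ = 1 − 0.88 = 12%, so p is recovered.
- *Binary rule requiring Month 24 or study completion for No.* Leavers with events stay Yes; event-free leavers become Unknown and are excluded. The proportion is [(1 − d)p + d·h] / [(1 − d) + d·h]: 0.1122/0.9042 = 12.4%, 0.1043/0.8083 = 12.9%, 0.0965/0.7125 = 13.5%. The error is now upward.

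**The case against.** **The composites are protected.** A reader might infer that early leavers also inflate NEDA-3, NEDA-4 or NEPAD. The documents do not support this. A composite Yes needs every component to be No; relapse No requires study completion, and MRI No requires late data. Subjects truncated for a delayed or never-started Course 2 are classified as if they had discontinued, and lack the late MRI data as well. This stands, and confines the point to three stand-alone rows.

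**Late worsening is not a defect of the No rule.** A reader might also infer that coding a first worsening at Month 24 as No is an error. It follows from requiring confirmation when no assessment is planned after Month 24. Kaplan-Meier would not count it either. With an assumed onset of 1% to 5% per six months and no leavers, three confirmable intervals give 2.97% to 14.26%, against 3.94% to 18.55% over four. That gap reflects what is being measured, and should be stated rather than treated as bias. What remains is that the plan does not show such cases separately.

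**The wording is formally correct.** The rows refer to the Treatment Period, which for an early leaver ends at the early-termination visit. No is then true for the time observed. This stands as wording, but the denominator still mixes follow-up lengths under a 24-month heading.

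**The size is assumed.** The model puts all leavers at Month 12 with nothing later. In practice an early-termination visit should include all three tests (Protocol 7.1.12), and those leaving after Month 18 lose less. Even so, the 12% example moves by only 0.8 to 2.3 percentage points. This stands: the direction is better supported than the size.

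**Conclusion.** The point holds for the stand-alone analyses of confirmed EDSS, T25FW and 9HPT progression. Subjects observed for about half of the planned 24 months can be counted as progression-free with no adjustment, so the proportions understate 24-month progression.

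The illustrated shortfall, about two thirds of the fraction followed only to Month 12, assumes even onset over Months 6 to 18 and leaving unrelated to progression. Leaving may well be informative: subjects who start another DMD after a relapse leave the trial (Protocol 5.5.1), and Course 2 may be delayed for lymphopenia. The documents give nothing with which to quantify that.

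The endpoints are tertiary, and Protocol 8.5.1 treats everything but the primary analysis as exploratory. The primary CUA analysis is not touched. The change is worth making because it is cheap and these rates are likely to be quoted on their own.

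**What to change.** - Analyse each of the three measures as time to first confirmed worsening. Censor at the last visit at which confirmation was still possible, and report the Kaplan-Meier estimate with its 95% confidence interval.
- State that, under the planned schedule, confirmable onset ends at Month 18.
- Apply the same censoring to subjects whose later data are set to missing because of Course 2. State that the estimate assumes non-informative censoring.
- Show first worsening at the last available visit as a separate unconfirmed count.
- Do not replace the rule with a binary one that requires Month 24 or study completion for No. It keeps leavers with events and drops those without, which biases the rate upward.

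The cost is SAP wording and one extra table per measure, using data already collected. The reported rates become slightly less favourable.
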